### 15.2.4 Fourth Secondary Objective

The secondary objective '*To present those AESIs that may be potentially related to Ozurdex reinjection*' will be assessed by the presence of the following AESIs:

- Cataract or lens opacities
- Glaucoma
- Hypotony
- Implant dislocation
- Infection vs. Non-infection related ocular inflammation
- Intraocular hypertension
- Mechanical failure of device and implant misplacement
- Ocular bleeding or hemorrhage
- Retinal detachment (tear or hole)
- Significant vitreous loss
- Vitreous detachment

These AESIs will be identified from eCRF section '*Adverse events*' (AE/F20 form) in which they are pre-listed.

All AESIs that began on or after the date of the first Ozurdex injection in the study eye will be considered for analysis. The analysis will be performed:

- considering all AESIs, AESIs that occur in the study eye, and AESIs that occur in the contralateral eye.
- cumulatively considering all AESIs and broken down by the number of injections, i.e. considering AESIs that occur after the first Ozurdex injection at baseline, AESIs that occur after the first Ozurdex reinjection, AESIs that occur after the second Ozurdex reinjection, etc. AESIs that occur on the same day of an Ozurdex injection will be considered as occurring after the injection.

AESIs will be summarized using descriptive statistics for the following parameters:

- Number and percentage (with 95% CI) of patients who experienced at least one AESI.

[REDACTED]

[REDACTED]

[REDACTED]

[REDACTED]

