### **10.5 Clinical Examinations**

Biomicroscopic and ophthalmomicroscopic exams performed in the study eye (yes/no), and intraocular pressure value measured in the study eye will be collected at baseline and at each visit occurred during the study period.

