#### **10.9.2 Collection and reporting of Safety Events by Investigators**

The study will be conducted in accordance with Directive 2001/83/EC, Regulation (EC) No 726/2004, Commission Implementing Regulation (EU) No 520/2012 as amended and detailed in GVP Modules VI.

Considering that study aims to explore the potential impact of recurrent Ozurdex injections, and not confirm the whole safety profile, and considering the current knowledge of the study drug safety profile, this study focuses only on the following AESIs (related or not to Ozurdex):

- **Glaucoma**, defined as damage to the optic nerve with progressive vision loss (open angle glaucoma, normal tension glaucoma, and acute angle closure glaucoma)
- **Intraocular hypertension**, defined as IOP without meeting the criteria for glaucoma
- **Hypotony**, defined as low IOP  $\leq 5$  mmHg
- **Cataract or lens opacities** (nuclear sclerotic, cortical and posterior subcapsular)
- **Ocular bleeding or hemorrhage** (conjunctival, anterior chamber, vitreous, macular, retinal)
- **Retinal detachment, tear or hole**
- **Vitreous detachment**
- **Infection vs. Non-infection related Ocular inflammation** (conjunctivitis, blepharitis, episcleritis, scleritis, keratitis, uveitis, retinitis and endophthalmitis)
- **Significant vitreous loss**
- **Mechanical failure of device and implant misplacement**
- **Implant dislocation**

In addition to AESIs, off-label use should be collected, and reported to Allergan whether or not off-label use was associated with an AE.

Due to the retrospective design of the study, the reporting of safety events to the sponsor is not solicited for this study. However, investigators are reminded about the possibility for them to report

any suspected ADRs directly to the marketing authorization holder of the suspected medicinal product (studied or not) or to the concerned competent authority via the national spontaneous reporting system.

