### 12.3 OPHTHALMOSCOPIC EXAMINATION

At baseline, the number and percentage of patients with ophthalmoscopic data available for the study eye will be described. Then, for patients with data available, the following parameters will be summarized using descriptive statistics:

- Any adverse findings (Yes, No)
- Macula pathology: edema (Present, Absent), hemorrhage (Present, Absent), exudate (Present, Absent), macular scarring (Present, Absent), drusen (Present, Absent), Choroidal neovascularization (CNV) (Present, Absent), cup to disc ratio.
- Vitreous: cells (Normal, +0.5, +1, +2, +3, +4), haze (Normal, +0.5, +1, +2, +3, +4), hemorrhage (Normal, +0.5, +1, +2, +3, +4), posterior detachment (Present, Absent). Findings on cells, haze and hemorrhage will also be described as 'Absent vs. Present' [DV].
- Peripheral retina: hemorrhage (Present, Absent), tear/holes (Present, Absent), laser treatment (Yes, No)

- Other macula pathology and peripheral retina findings will be described by PT (MedDRA version 21.1). If several pathologies/findings with the same PT are reported for the same patient, s/he will be counted once for that PT.

During the follow-up period, the number and percentage of patients having at least one adverse finding in the study eye (Yes, No) [DV] will be described. Then, for all patients with at least one adverse finding, the type of adverse finding will be described as 'Present, absent' for each pre-listed category (macula pathology (edema, hemorrhage, exudate, etc), vitreous (cells, haze, etc), peripheral retina (hemorrhage, tear/holes, etc)) as well as for adverse findings reported as other macula pathology and peripheral retina. If an adverse finding has been identified more than once for the same category for the same patient, s/he will be counted once for that category. For patients with at least one adverse finding during the follow-up period, a listing will also be presented with results of ophthalmoscopic examination at baseline and during the follow-up period.

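### AESIs are taken from the adverse event form alone, so a recorded IOP of 5 mmHg or less that is not also entered there is counted in no visible SAP output

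*SAP*

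**What the plan says.** Protocol 10.9.2 limits safety collection to a fixed list: "this study focuses only on the following AESIs (related or not to Ozurdex"). Hypotony is "defined as low IOP" of 5 mmHg or less, the only entry on the list with a numeric rule. Other entries are named conditions that are seen at examination, such as lens opacities ("nuclear sclerotic, cortical and posterior subcapsular"), haemorrhage by site, "Retinal detachment, tear or hole", and vitreous detachment.

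Protocol 10.5 states that the "intraocular pressure value measured in the study eye will be collected at baseline and at each visit occurred during the study period".

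SAP 15.2.4 sets the source for the AESI analysis: "These AESIs will be identified from eCRF section" for adverse events, cited as "AE/F20 form) in which they are pre-listed". AESIs that began on or after the first injection count, and they are broken down by number of injections. SAP 16.0 says the safety analysis is covered by 15.2.4.

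The examination data have separate analyses. SAP 12.3, for example, lists "Peripheral retina: hemorrhage (Present, Absent), tear/holes (Present, Absent), laser treatment (Yes, No") among the ophthalmoscopy items, and describes follow-up findings by category with patient listings.

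**The concern.** The AESI list mixes diagnoses with findings, and hypotony is purely a reading. The reading is in the database, yet it becomes an AESI only if the site also enters it on a second form. No visible rule derives an AESI from the IOP, biomicroscopy or ophthalmoscopy data, and none compares those forms with AE/F20. SAP 22.0 mentions no change on the point.

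At stake is the AESI percentage, the output of a stated secondary objective. Protocol 7.3.3 and SAP 7.0 also intend to set the safety events against the literature, to judge background risk against an effect of Ozurdex. Incomplete ascertainment would push that comparison towards reassurance. Hypotony matters here because Protocol 5.1 lists it among the reactions linked to the injection procedure.

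**Working it through.** The documents give no AESI rate and no agreement rate between forms, so there is no plan figure to reproduce. The check sets the passages side by side.

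**1. Where each finding is held and what the SAP does with it**

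| AESI (Protocol 10.9.2) | Examination data | Visible SAP output other than AE/F20 | What is missing |
|---|---|---|---|
| Hypotony | Study-eye IOP at each visit | 12.4: levels at baseline and 7-12 weeks, changes, and a figure of means that adds reinjection visits | Any count at or below 5 mmHg; any listing |
| Haemorrhage | Biomicroscopy (subconjunctival); ophthalmoscopy (macular, vitreous, peripheral) | 12.2-12.3: present/absent at follow-up, with listings | Not an AESI, not new since baseline, not by injection number |
| Vitreous detachment | Ophthalmoscopy | 12.3, same | Same |
| Retinal tear or hole | Ophthalmoscopy | 12.3, same | Same |
| Cataract or lens opacity | Lens form: opacity and grade at baseline; a question on change in lens status at follow-up | 12.1: phakic to pseudophakic; 13.4: cataract surgery | Routine opacity grading at follow-up is not shown to be collected |

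Hypotony is the only row with a numeric definition, values at each visit and no count anywhere.

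**2. One case traced through the SAP**

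Suppose an IOP of 4 mmHg is recorded on Day 7 after an injection and is not entered on AE/F20.
- Protocol 10.9.2: it qualifies, because 4 is not above 5.
- SAP 15.2.4: it is not counted, because the source is AE/F20.
- SAP 12.4 with 21.2: the window is 7-12 weeks plus or minus 2 weeks. That gives (7 - 2) x 7 = Day 35 to (12 + 2) x 7 = Day 98, so Day 7 is outside it.

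If the same value falls inside the window with a second reading x, the SAP uses (4 + x)/2, which exceeds 5 whenever x is above 6. If it is the only reading in the window, it can appear as the minimum in the descriptive statistics, but not as a number of patients with hypotony.

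**3. Reconciliation of the forms**

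Protocol 12 issues no queries once data are entered, because sites can no longer link a record to a patient. Disagreement between forms can then be examined only in the analysis.

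**4. Scale (illustration only)**

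With n = 150, the planned size, each patient missed lowers a percentage by 1/150 = 0.67 points. SAP 21.1 specifies Clopper-Pearson intervals. With no patient counted the upper limit is 1 - 0.025^(1/150) = 2.4%. For assumed true counts:

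| Patients | Percentage | Exact 95% CI |
|---|---|---|
| 0 | 0% | 0 to 2.4% |
| 3 | 2.0% | 0.4 to 5.7% |
| 8 | 5.3% | 2.3 to 10.2% |
| 15 | 10.0% | 5.7 to 16.0% |

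The counts of 3, 8 and 15 are assumptions and say nothing about the likely number missed.

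**The case against.** The best defence is that an adverse event form with the AESIs pre-listed is a legitimate source. The abstractor is prompted term by term, so the chart need not use the label adverse event. Protocol 7.3.2 adds automated consistency controls and review of all entries by the principal investigator. Protocol 10.9.1.4 defines an AESI as a kind of adverse event, and Protocol 14.2.2.3.4 does not ask for derivation from examination data. All of this stands. It means the SAP does not contradict the protocol, and that a finding is lost only when it is entered on an examination form and not on AE/F20. But neither document says that any automated control links an IOP value to AE/F20.

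A reader might infer that examination findings in general go uncounted. The documents do not support that. SAP 12.2-12.3 tabulate haemorrhage, posterior detachment and tear or hole at follow-up, with listings that show baseline beside follow-up, and SAP 13.4 tabulates cataract surgery.

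A reader might also infer that new or worsening lens opacities are collected and ignored. SAP 12.1 and 21.3.3 describe opacity and grade at baseline. At follow-up they show a question on change in lens status, with raw lens-form data where a change was reported. Whether opacity is graded at follow-up cannot be seen.

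**Conclusion.** The point holds in a limited form. A study-eye IOP of 5 mmHg or less that is not also entered on AE/F20 meets the protocol's definition of hypotony and is counted in no visible SAP output. For haemorrhage, posterior vitreous detachment and retinal tear or hole the gap is narrower: the findings are reported, but outside the AESI analysis and without a new-since-baseline rule or a breakdown by injection.

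The size of any undercount is unknown. It is tempting to apply a miss rate to the 67.9% cataract rate in Protocol 5.1, but that does not work. The figure is itself a rate of reported adverse events, from three-year trials, whereas follow-up here may be as short as 12 months and the protocol says cataract events rose after the first year. The documents give no miss rate either.

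Two reservations apply. Lines after the summary parameters in SAP 15.2.4 are redacted, and table specifications are in a separate document. A source rule there seems unlikely but cannot be excluded. The examination data discussed here concern the study eye, so contralateral-eye AESIs cannot be checked this way.

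**What to change.** Keep the AE/F20 analysis in SAP 15.2.4 as planned. Beside it, add a supplementary study-eye row, labelled AE/F20 or examination finding, defined as follows:

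- Hypotony: any recorded post-injection IOP of 5 mmHg or less, using individual readings, not window means.
- Vitreous haemorrhage, posterior vitreous detachment, and retinal tear or hole: present at follow-up and recorded absent at baseline. Show patients with no baseline examination separately.
- For each, give the number of patients identified by AE/F20 only, by examination only, and by both.

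If the row is broken down by injection number, state how an IOP from a reinjection day is assigned. SAP 12.4 takes that value as measured before the injection, whereas SAP 15.2.4 treats same-day AESIs as occurring after it.

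Do not derive a graded lens-opacity row unless the lens form is confirmed to capture opacity at follow-up. Instead, cross-tabulate cataract AESIs with the cataract surgery and phakic-to-pseudophakic change already planned.

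The cost is SAP wording and programming from collected data. The downside is that the supplementary row may include findings caused by the diabetic eye disease itself, so it stands beside the AE/F20 row and does not replace it.

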### **10.6 Contralateral Eye**

DME status in the contralateral eye will be recorded at baseline and at all visits occurred during the study period.

Treatments for DME received prior to study period will be recorded for the contralateral eye. For each visit occurred during the study period, treatments received in the contralateral eye (inclusive of intravitreal treatment) will be recorded.

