## **15.0 ANALYSES OF THE OBJECTIVES OF THE STUDY**

### **15.1 ANALYSIS OF THE PRIMARY OBJECTIVE**

The primary objective '*To assess reinjection interval of Ozurdex implants in patients with DME in real-world in Germany and Switzerland*' will be assessed by the following outcomes:

- Total number of Ozurdex reinjections in the study eye during follow-up, and considering years after the first Ozurdex injection in the study eye (See definition in Table 21-1).
- Re[injection interval defined in months as: (Date of injection (j+1) – Date of injection j) ÷ (365.25÷12), for j=1,...,n where n is the number of reinjections in the study eye. The result will be rounded to 0.1.

The number of Ozurdex reinjections in the study eye per year will be first summarized using descriptive statistics for the following parameters:

- The total number and percentage of Ozurdex reinjections received during follow-up.
- Number and percentage (with 95% CI) of patients with at least one Ozurdex reinjection during Year 1 (See definition in Table 21-1), and number of reinjections per patient during Year 1, for all patients in the analysis population. Note: the first Ozurdex injection will not be considered here, only reinjections will be counted.
- Number and percentage (with 95% CI) of patients with at least one Ozurdex reinjection and number of reinjections per patient during Year k (k=2, 3), for patients having a complete Year k of follow-up (see definition of 'Complete year' in Section 21.2).
- Number and percentage of patients receiving each Ozurdex reinjection (first, second, third, etc) for each year of follow-up (Year k, k=1 to 3) considering patients having the complete year of follow-up.

The Ozurdex reinjection interval in the study eye will be described using descriptive statistics for the following parameters:

- Re[injection interval (months) considering all eligible reinjections recorded in the EDC. The 95% CI of the mean will also be presented.
- Re[injection interval (months) considering each reinjection separately (i.e. first reinjection, second reinjection, etc). 95% CI of the mean will also be presented.

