## **21.2 STUDY PERIODS**

### Baseline

The baseline is defined as the day of the first Ozurdex implant injection in the study eye.

The baseline time period is defined as the 3-month period prior to the first Ozurdex injection in the study eye. This 3-month period prior to first Ozurdex injection in the study eye applies to assessments of prior ocular surgical history and treatments, IOP, BCVA, and CRT measures.

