## **22.0            CHANGES TO ANALYSES SPECIFIED IN PROTOCOL**

The changes to the analyses specified in the original protocol, dated 24 July 2018, are specified below:

In protocol Section 14.2.2.3.2 it is specified that reason of initial injection and for reinjection will be described. Reason for initial injection is not collected in the eCRF and therefore only reason for reinjection will be described.

No analyses will be performed on the contralateral eye with the exception of AESIs (Section 15.2.4) and select measures of ophthalmic history and current ophthalmic conditions (Section 10.2).

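### The breakdown of AESIs by injection number includes contralateral-eye events but counts study-eye injections, with no visible rule matching the eye of the event to the eye injected

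*SAP*

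**What the plan says.** SAP 15.2.4 sets out the AESI analysis in two bullets. The first gives the eye groupings: "considering all AESIs, AESIs that occur in the study eye, and AESIs that occur in the contralateral eye". The second gives the injection dimension: "cumulatively considering all AESIs and broken down by the number of injections, i.e. considering AESIs that occur after the first Ozurdex injection at baseline", and so on through the later reinjections. One date opens the window for events in either eye: "All AESIs that began on or after the date of the first Ozurdex injection in the study eye will be considered for analysis".

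The second bullet does not name the eye whose injections are counted, but other sections do. SAP 21.2 states: "The baseline is defined as the day of the first Ozurdex implant injection in the study eye". SAP 15.1 defines the reinjection interval over a series "where n is the number of reinjections in the study eye". Protocol 10.7 asks for implant dates in the study eye.

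SAP 21.3.4 derives the days from the last Ozurdex injection to AESI onset. It takes the latest injection on or before onset and does not say in which eye.

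For the other eye, protocol 10.6 provides that, visit by visit, "treatments received in the contralateral eye (inclusive of intravitreal treatment) will be recorded". SAP 22.0 then says: "No analyses will be performed on the contralateral eye with the exception of AESIs", with a second exception for selected ophthalmic history and current conditions. No analysis of the contralateral eye's own Ozurdex exposure is described.

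**The concern.** The listed AESIs are ocular and almost all local to one eye. Protocol 5.1 reports no systemic adverse drug reactions with Ozurdex apart from headache and migraine, and says that procedure-related events rise in proportion to the number of treatments. Numbering a contralateral event by injections given to the other eye therefore has no useful reading. The plainest cases are implant dislocation and device failure or misplacement: in the contralateral eye these can come only from an implant placed in that eye.

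The fourth secondary objective concerns AESIs potentially related to reinjection, and protocol 10.9.2 gives the effect of repeated injections as the reason for collecting AESIs. SAP 16.0 makes 15.2.4 the whole of the safety analysis. The breakdown by injection number is the output that serves this aim most directly, and in its all-AESI form it mixes events that followed a study-eye reinjection with events that have no such link.

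**Working it through.** The plan states no figure on this point, so the check is a reading of the text followed by an illustration.

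**Which eye each element refers to**

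| Element | Source | Eye |
|---|---|---|
| Events entering the all-AESI set | SAP 15.2.4 | Both |
| Opening of the AESI window | SAP 15.2.4 | Study eye |
| Baseline, where the injection count starts | SAP 21.2 | Study eye |
| Reinjections that are numbered | SAP 15.1 | Study eye |
| Implant dates collected as such | Protocol 10.7 | Study eye |
| Last injection before onset | SAP 21.3.4 | Not stated |
| Contralateral treatments | Protocol 10.6 | Contralateral, by visit |

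The events come from both eyes, while the counter comes from the study eye. Nothing visible matches the two.

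**Can a contralateral eye have implants of its own?** Yes. Protocol 8.2 provides for patients in whom both eyes meet the inclusion criteria and makes the eye with more Ozurdex injections the study eye. An illustration must respect that rule.

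**Illustration (all dates assumed).** Study-eye implants on days 1, 150 and 300; one contralateral implant on day 200; contralateral AESI on day 250. The study eye has three implants against one. The SAP 21.3.4 formula is onset date minus date of last injection.

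- Study-eye count: the last study-eye implant on or before day 250 is the second, on day 150. The event is tabulated after the first reinjection, with a time of 250 − 150 = 100 days.
- The eye's own exposure: the last contralateral implant is its first, on day 200. The time is 250 − 200 = 50 days, and that eye has had no reinjection.
- If the contralateral eye had never received an implant, the event would still be tabulated after the first reinjection at 100 days, although that eye's exposure is zero.

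**The other reading of SAP 21.3.4.** If the last injection may be in either eye, the contralateral event gets 50 days. But a study-eye AESI on day 250 would then also get 250 − 200 = 50 days, counted from an implant in the other eye, instead of 100. Neither reading works for both eyes without a matching rule.

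**Size.** The number of misfiled events depends on the contralateral AESI rate and on the share of patients with implants in both eyes. The documents give neither, so no overall figure can be derived.

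**The case against.** The strongest reply is that this is loose wording rather than a wrong rule. The two bullets in SAP 15.2.4 are separate, and the text does not say that the eye groupings are crossed with injection number. The study-eye count is inferred from the definition of baseline. Some parameters in 15.2.4 are blacked out, and SAP 4.0 places the table specifications in a separate document, so the two dimensions may be combined sensibly there. A study-eye grouping is already planned, the objective is descriptive and secondary, and protocol 8.2 disclaims causal conclusions.

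Much of this stands. A reader might infer that the SAP prescribes a contralateral-only table by study-eye injection number; the text does not say so. The point does not need it, because contralateral events sit inside the all-AESI set that the second bullet breaks down. The blacked-out text cannot be judged either way, so the point rests on the visible rules alone.

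Three other stronger readings also fail. A reader might say that the all-AESI percentage is inflated, but it is a labelled total planned alongside a study-eye figure, and any stated excess would rest on invented rates. A reader might picture a contralateral eye with more implants than the study eye, but where both eyes qualify the study-eye rule excludes that. And a reader might say that the contralateral eye's treatment is not captured; protocol 10.6 does record it, and what is absent is its use in the analysis.

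**Conclusion.** The point holds for the breakdown by injection number and for the time since last injection. As written, SAP 15.2.4 numbers all AESIs, including contralateral-eye events, by an injection count that on the SAP's own definitions belongs to the study eye, and SAP 21.3.4 does not say which eye's injection counts. In the illustration a contralateral event is shown after a reinjection at 100 days when it came 50 days after that eye's first implant. Those dates are assumed, and the frequency of such cases cannot be estimated from the documents.

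Cumulative study-eye results are not affected. The conclusion assumes that baseline in 15.2.4 carries its SAP 21.2 meaning and that no eye-matching rule lies in the blacked-out lines or the separate table specifications. The correction is worth making because this is the only safety analysis, but it bears on a descriptive secondary objective and not on the primary one.

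**What to change.** In SAP 15.2.4, state that the breakdown by injection number uses AESIs in the study eye and injections in the study eye. In SAP 21.3.4, add the same restriction to the time from last injection to AESI. Report contralateral AESIs, and the all-AESI total, cumulatively only.

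Where the visit-level treatment data of protocol 10.6 allow, split contralateral AESIs by whether that eye had received Ozurdex on or before the event. This part should be conditional. Protocol 10.7 requests implant dates for the study eye only, and the SAP defines no variable for contralateral Ozurdex. The per-eye counts in the screening log cannot be linked to study patients (SAP 9.0), and no queries can be sent to sites (protocol 12). If contralateral implants cannot be identified reliably, drop the split; the main restriction still works.

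The cost is SAP wording and table shells, with no new data collection. The downside is that contralateral AESIs lose the breakdown by injection number.
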